10.2 Appendix 2 - Additional Safety Guidance

Further Guidance on the Definition of a Serious Adverse Event

Life-threatening

'Life-threatening' means that the subject was at immediate risk of death from an AE as it occurred or it is suspected that use or continued use of the investigational product would result in the subject's death. 'Life-threatening' does not mean that had an AE occurred in a more severe form it might have caused death (eg, hepatitis that resolved without hepatic failure).

Hospitalization

Outpatient treatment in an emergency room is not in itself a serious AE, although the reasons for it may be (eg, bronchospasm, laryngeal edema). Hospital admissions and/or surgical operations planned before or during a study are not considered AEs if the illness or disease existed before the subject was enrolled in the study, provided that it did not deteriorate in an unexpected way during the study.

Important Medical Event or Medical Intervention

Medical and scientific judgment should be exercised in deciding whether a case is serious in situations where important medical events may not be immediately life threatening or result in death, hospitalization, disability or incapacity but may jeopardize the subject or may require medical intervention to prevent one or more outcomes listed in the definition of serious. These should usually be considered as serious.

Simply stopping the suspect drug does not mean that it is an important medical event; medical judgment must be used.

Examples of such events are:

- Angioedema not severe enough to require intubation but requiring IV hydrocortisone treatment
- Hepatotoxicity caused by paracetamol (acetaminophen) overdose requiring treatment with N-acetylcysteine
- Intensive treatment in an emergency room or at home for allergic bronchospasm
- Blood dyscrasias (eg, neutropenia or anemia requiring blood transfusion) or convulsions that do not result in hospitalization
- Development of drug dependency or drug abuse

Assessment of Severity

Assessment of severity is one of the responsibilities of the investigator in the evaluation of AEs and SAEs. The determination of severity should be made by the investigator based upon medical judgment and the severity categories of Grades 1 to 5 as defined below.

Grade 1	An event of mild intensity that is usually transient and may require only minimal treatment or therapeutic intervention. The event does not generally interfere with usual activities of daily living.
Grade 2	An event of moderate intensity that is usually alleviated with additional specific therapeutic intervention. The event interferes with usual activities of daily living, causing discomfort but poses no significant or permanent risk of harm to the subject.
Grade 3	A severe event that requires intensive therapeutic intervention. The event interrupts usual activities of daily living, or significantly affects the clinical status of the subject.
Grade 4	An event, and/or its immediate sequelae, that is associated with an imminent risk of death or with physical or mental disabilities that affect or limit the ability of the subject to perform activities of daily living (eating, ambulation, toileting, etc).
Grade 5	Death (loss of life) as a result of an event.

It is important to distinguish between serious criteria and severity of an AE. Severity is a measure of intensity whereas seriousness is defined by the criteria in Section 5.2. A Grade 3 AE need not necessarily be considered an SAE. For example, a Grade 3 headache that persists for several hours may not meet the regulatory definition of an SAE and would be considered a nonserious event, whereas a Grade 2 seizure resulting in a hospital admission would be considered an SAE.

Assessment of Relationship

Relationship to Investigational Product

The investigator is required to provide an assessment of relationship of AEs and SAEs to the investigational product. The following factors should be considered when deciding if there is a "reasonable possibility" that an AE may have been caused by the investigational product.

- Did the subject actually receive the suspect investigational product? Did the AE occur in a reasonable temporal relationship to the administration of the suspect investigational product?
- Consistency with known investigational product profile. Was the AE consistent with the previous knowledge of the suspect investigational product (pharmacology and toxicology) or products of the same pharmacological class, OR could the AE be anticipated from its pharmacological properties? Is this event frequently observed in the study population regardless of treatment?
- De-challenge experience. Did the AE resolve or improve on stopping or reducing the dose of the suspect investigational product?
- No alternative cause. The AE cannot be reasonably explained by another etiology such as the underlying disease, other drugs, or other host or environmental factors.
- Re-challenge experience. Did the AE reoccur if the suspected investigational product was reintroduced after having been stopped? MedImmune would not normally recommend or support a re-challenge.
- Laboratory tests. Did a specific laboratory investigation (if performed) confirm the relationship?

A "reasonable possibility" could be considered to exist for an AE where one or more of these factors exist.

If available information describing the event and the circumstances is insufficient to make a definitive assessment of causal association the nature of AE, and likelihood of this event occurring in the study population should be taken into account (eg, events not typically seen in the study population are more likely to lack an alternative explanation).

In contrast, there would not be a "reasonable possibility" of causality if none of the above criteria apply or where there is evidence of exposure and a reasonable time course but any de-challenge (if performed) is negative or ambiguous or there is another more likely cause of the AE.

In difficult cases, other factors could be considered such as:

- Is this a recognized feature of overdose of the investigational product?
- Is there a known mechanism? Ambiguous cases should be considered as being a "reasonable possibility" of a causal relationship unless further evidence becomes available to refute this. Causal relationship in cases where the disease under study has deteriorated due to lack of effect should be classified as "no reasonable possibility".

Relationship to Protocol Procedures

The investigator is also required to provide an assessment of relationship of SAEs to protocol procedures on the SAE Report Form. This includes non-TESAEs (ie, SAEs that occur prior to the administration of investigational product) as well as TESAEs. A protocol-related SAE may occur as a result of a procedure or intervention required during the study (eg, blood collection, washout of an existing medication). The following guidelines should be used by investigators to assess the relationship of SAEs to the protocol:

- Protocol related: The event occurred due to a procedure/intervention that was described in the protocol for which there is no alternative etiology present in the subject's medical record.
- Not protocol related: The event is related to an etiology other than the procedure/ intervention that was described in the protocol (the alternative etiology must be documented in the study subject's medical record).

10.3 Appendix 3 - National Institute of Allergy and Infectious Diseases and Food Allergy and Anaphylaxis Network Guidance for Anaphylaxis Diagnosis

NIAIDs and FAAN define anaphylaxis as a serious allergic reaction that is rapid in onset and may cause death. They recognize 3 categories of anaphylaxis, with criteria designated to capture from 80% of cases (category 1) to > 95% of all cases of anaphylaxis (for all 3 categories).

1. Acute onset of an illness (minutes to several hours) with involvement of the skin, mucosal tissue, or both (eg, generalized hives, pruritus or flushing, swollen lips-tongue-uvula)

AND AT LEAST ONE OF THE FOLLOWING

- a. Respiratory compromise (eg, dyspnea, wheeze-bronchospasm, stridor, reduced peak expiratory flow [PEF], hypoxemia)
- b. Reduced BP or associated symptoms of end-organ dysfunction (eg, hypotonia [collapse], syncope, incontinence)
- 2. Two or more of the following that occur rapidly after exposure to a likely allergen for that patient (minutes to several hours):
 - a. Involvement of the skin-mucosal tissue (eg, generalized hives, itch-flush, swollen lips-tongue-uvula)
 - a. Respiratory compromise (eg, dyspnea, wheeze-bronchospasm, stridor, reduced PEF, hypoxemia)
 - b. Reduced BP or associated symptoms (eg, hypotonia [collapse], syncope, incontinence)
 - c. Persistent gastrointestinal symptoms (eg, crampy abdominal pain, vomiting)
- 3. Reduced BP after exposure to known allergen for that patient (minutes to several hours):
 - a. Infants and children: low systolic BP (age specific) or greater than 30% decrease in systolic BP
 - b. Adults: systolic BP of less than 90 mm Hg or greater than 30% decrease from that person's baseline

10.4 Appendix 4 - Actions Required in Cases of Increases in Liver Biochemistry and Evaluation of Hy's Law

10.4.1 Introduction

This appendix describes the process to be followed in order to identify and appropriately report cases of HL. It is not intended to be a comprehensive guide to the management of elevated liver biochemistries.

During the course of the study the investigator will remain vigilant for increases in liver biochemistry. The investigator is responsible for determining whether a subject meets potential HL (PHL) criteria at any point during the study.

The investigator participates, together with MedImmune clinical project representatives, in review and assessment of cases meeting PHL criteria to agree whether HL criteria are met. HL criteria are met if there is no alternative explanation for the elevations in liver biochemistry other than drug-induced liver injury (DILI) caused by the investigational product.

The investigator is responsible for recording data pertaining to PHL/HL cases and for reporting AEs and SAEs according to the outcome of the review and assessment in line with standard safety reporting processes.

10.4.2 Definitions

10.4.2.1 Potential Hy's Law

AST or $ALT \ge 3 \times ULN$ together with $TBL \ge 2 \times ULN$ at any point during the study following the start of investigational product irrespective of an increase in ALP.

10.4.2.2 Hy's Law

AST or $ALT \ge 3 \times ULN$ together with $TBL \ge 2 \times ULN$, where no other reason, other than the investigational product, can be found to explain the combination of increases; eg, elevated ALP indicating cholestasis, viral hepatitis, another drug.

For PHL and HL the elevation in transaminases must precede or be coincident with (ie, on the same day) the elevation in TBL, but there is no specified timeframe within which the elevations in transaminases and TBL must occur.

10.4.2.3 Identification of Potential Hy's Law Cases

In order to identify cases of PHL, it is important to perform a comprehensive review of laboratory data for any subject who meets any of the following identification criteria in isolation or in combination:

- ALT \geq 3 × ULN
- AST \geq 3 × ULN
- TBL $\geq 2 \times ULN$

When a subject meets any of the identification criteria, in isolation or in combination, the central laboratory will immediately send an alert to the investigator (also sent to sponsor study representative).

The investigator will also remain vigilant for any local laboratory reports where the identification criteria are met, where this is the case the investigator will:

- Notify the sponsor study representative
- Request a repeat of the test (new blood draw) by the central laboratory
- Complete the appropriate unscheduled laboratory eCRF module(s) with the original local laboratory test result

When the identification criteria are met from central or local laboratory results the investigator will without delay:

• Determine whether the subject meets PHL criteria by reviewing laboratory reports from all previous visits (including both central and local laboratory results)

The investigator will, without delay, review each new laboratory report and if the identification criteria are met will:

- Notify the sponsor study representative
- Determine whether the subject meets PHL criteria by reviewing laboratory reports from all previous visits

10.4.3 Follow-up

10.4.3.1 Potential Hy's Law Criteria Not Met

If the subject does not meet PHL criteria the investigator will:

- Inform the study representative that the subject has not met PHL criteria
- Perform follow-up on subsequent laboratory results according to the guidance provided in the study protocol.

10.4.3.2 Potential Hy's Law Criteria Met

If the subject does meet PHL criteria the investigator will:

- Determine whether PHL criteria were met at any study visit prior to starting study treatment
- Notify the sponsor study representative who will then inform the study team

The medical monitor contacts the investigator, to provide guidance, discuss and agree an approach for the study subjects' follow-up and the continuous review of data. Subsequent to this contact the investigator will:

- Monitor the subject until liver biochemistry parameters and appropriate clinical symptoms and signs return to normal or baseline levels, or as long as medically indicated
- Investigate the etiology of the event and perform diagnostic investigations as discussed with the medical monitor. This includes deciding which tests available in the HL laboratory kit should be used.
- If at any time (in consultation with the medical monitor) the PHL case meets serious criteria, report it as an SAE using standard reporting procedures

10.4.4 Review and Assessment of Potential Hy's Law Cases

The instructions in this section should be followed for all cases where PHL criteria are met.

No later than 3 weeks after the biochemistry abnormality was initially detected, the medical monitor will contact the investigator in order to review available data and agree on whether there is an alternative explanation for meeting PHL criteria other than DILI caused by the investigational product. The medical monitor and Global Safety Physician will also be involved in this review together with other subject matter experts as appropriate.

According to the outcome of the review and assessment, the investigator will follow the instructions below.

If there is an agreed alternative explanation for the ALT or AST and TBL elevations, a determination of whether the alternative explanation is an AE will be made and subsequently whether the AE meets the criteria for an SAE:

- If the alternative explanation is not an AE, record the alternative explanation according to the Medical Monitoring Plan
- If the alternative explanation is an AE/SAE, record the AE /SAE in the CRF accordingly and follow the sponsor's standard processes

If it is agreed that there is **no** explanation that would explain the ALT or AST and TBL elevations other than the investigational product:

- Report an SAE (report term 'Hy's Law') according to sponsor's standard processes.
 - The 'Medically Important' serious criterion should be used if no other serious criteria apply
 - As there is no alternative explanation for the HL case, a causality assessment of 'related' should be assigned.

If, there is an unavoidable delay, of over 3 weeks, in obtaining the information necessary to assess whether or not the case meets the criteria for HL, then it is assumed that there is no alternative explanation until such time as an informed decision can be made:

- Report an SAE (report term 'Potential Hy's Law') applying serious criteria and causality assessment as per above
- Continue follow-up and review according to agreed plan. Once the necessary supplementary information is obtained, repeat the review and assessment to determine whether HL criteria are met. Update the SAE report according to the outcome of the review.

10.4.5 Actions Required When Potential Hy's Law Criteria Are Met Before and After Starting Study Treatment

This section is applicable to subjects with liver metastases who meet PHL criteria on study treatment having previously met PHL criteria at a study visit prior to starting study treatment.

At the first on-study treatment occurrence of PHL criteria being met the investigator will:

- Determine if there has been a significant change in the subjects' condition compared with the last visit where PHL criteria were met
 - If there is no significant change no action is required
 - If there is a significant change, notify the study representative, who will inform the central study team, then follow the subsequent process described in Section 10.4.3.2

A 'significant' change in the subject's condition refers to a clinically relevant change in any of the individual liver biochemistry parameters (ALT, AST, or TBL) in isolation or in combination, or a clinically relevant change in associated symptoms. The determination of whether there has been a significant change will be at the discretion of the investigator; this may be in consultation with the medical monitor if there is any uncertainty.

10.4.6 Actions Required for Repeat Episodes of Potential Hy's Law

This section is applicable when a subject meets PHL criteria on study treatment and has already met PHL criteria at a previous on-study treatment visit.

The requirement to conduct follow-up, review, and assessment of a repeat occurrence(s) of PHL is based on the nature of the alternative cause identified for the previous occurrence.

The investigator should determine the cause for the previous occurrence of PHL criteria being met and answer the following question:

• Was the alternative cause for the previous occurrence of PHL criteria being met found to be the disease under study, eg, chronic or progressing malignant disease, severe infection, or liver disease, or did the subject meet PHL criteria prior to starting study treatment and at their first on study treatment visit as described in Section 10.4.5?

If No: Follow the process described in 10.4.3.1

If Yes: Determine if there has been a significant change in the subject's condition compared with when PHL criteria were previously met:

- If there is no significant change no action is required
- If there is a significant change follow the process described in Section 10.4.3.2

A 'significant' change in the subject's condition refers to a clinically relevant change in any of the individual liver biochemistry parameters (ALT, AST, or TBL) in isolation or in combination, or a clinically relevant change in associated symptoms. The determination of

whether there has been a significant change will be at the discretion of the investigator; this may be in consultation with the medical monitor if there is any uncertainty.

10.5 Appendix 5 – Diagnosis of a Potential Thromboembolic Event

10.5.1 Clinical Probability Score of Deep Vein Thrombosis - Wells Criteria

DVT: Wells	
Variable	Points
Active cancer (treatment ongoing or within previous 6 mo or palliative)	1
Paralysis, paresis, or recent plaster immobilization of the lower extremities	1
Recently bedridden for more than 3 d or major surgery within 4 wk	1
Localized tenderness along distribution of the deep venous system	1
Entire leg swollen	1
Calf swelling by more than 3 cm compared with asymptomatic leg (measured 10 cm below tibial tuberosity)	1
Pitting edema (greater in the symptomatic leg)	1
Collateral superficial veins (nonvaricose)	1
Past history of DVT	1
Alternative diagnosis as likely or greater than that of DVT	-2

d = days; DVT = deep vein thrombosis; mo = months; wk = weeks Score $\leq 1 =$ DVT is clinically unlikely; Score $\geq 2 =$ DVT is clinically likely

Algorithm for Suspected Deep Vein Thrombosis

In every case of a clinically suspected deep vein thrombosis (DVT), the clinical probability score must be calculated using by the aforementioned Wells criteria and a D-dimer test must be performed.

- If clinical probability shows "DVT unlikely" (ie, score ≤ 1), and D-dimer value is ≤ ULN, DVT is excluded.
- If clinical probability shows "DVT unlikely" (ie, score ≤ 1), and D-dimer value is > ULN, compression ultrasound will be performed.
 - If ultrasound shows no abnormal changes, DVT is excluded.
 - If ultrasound shows abnormal changes, compatible with thrombosis, DVT is confirmed.
 - If ultrasound is unavailable/equivocal and D-dimer is only increased at the time of event, DVT is considered "likely".
- If clinical probability shows "DVT likely" (ie, score ≥ 2), compression ultrasound will be performed irrespective the D-dimer value.
 - If ultrasound shows no abnormal changes, ultrasound should be repeated within 7 days; if ultrasound again shows no abnormal changes, DVT is excluded.

- If ultrasound shows abnormal changes compatible with thrombosis, DVT is confirmed.
- If ultrasound is unavailable or equivocal, DVT is considered "likely".
- Each situation that cannot be adjudicated using the algorithm above will be considered as "DVT likely" and dose escalation will be suspended.

10.5.2 Clinical Probability Score of Pulmonary Embolism - Wells Criteria

PE: Wells			
Variable	Points		
Signs or symptoms of DVT Alternative diagnosis is less likely than PE	3 3		
Heart rate > 100 bpm Immobilization/surgery in previous 4 wk Prior history of DVT or PE Hemoptysis	1.5 1.5 1.5 1		
Active cancer	1		

bpm = beats per minute; DVT = deep vein thrombosis; PE = pulmonary embolism; wk = week Score $\leq 4 =$ PE is clinically unlikely; Score $\geq 4 =$ PE is clinically likely

Algorithm for Suspected Pulmonary Embolism:

In every case of suspected pulmonary embolism (PE), clinical probability score must be calculated using by the aforementioned Wells criteria and a D-dimer test must be performed.

- If clinical probability shows "PE unlikely" (ie, score ≤ 4), and D-Dimer value is ≤ ULN, PE is excluded.
- If clinical probability shows "PE likely" (ie, score ≥ 4) or D-dimer value is > ULN, chest X-Ray will be performed.
 - If chest X-ray is normal, a ventilation-perfusion (V/Q) scan will be performed.
 - If chest X-Ray is abnormal, computerized tomographic pulmonary angiography (CTPA) will be considered.
 - If V/Q scan or CTPA are not available or equivocal, PE is considered "likely" unless clinical probability shows "PE unlikely" and D-dimer is > ULN at previous time points during the study, including at baseline.
- Each situation that cannot be adjudicated using the algorithm above will be considered as "PE likely" and dose escalation will be suspended.

Adapted from Wells P and Anderson D. The diagnosis and treatment of venous thromboembolism. Hematology Am Soc Hematol Educ Program. 2013;2013:457-63.

Document Name:	protocol-d5100c00002-amendment-3-clean			
Document Title:	protocol-d5100c00002-amendment-3-clean			
Document ID:	Doc ID-003702578			
Version Label:	1.0 Approved CURRENT LATEST			
Server Date (dd-MMM-yyyy HH:	mm 'GMT'Z)	SignedBy	Meaning of Signature	
02-Oct-2017 08:56 GMT+0100		PPD	Biostatistics Approval	
02-Oct-2017 08:56 GMT+0100		PPD	Clinical Operations Approval	
02-Oct-2017 10:45 G	MT+0100	PPD	Medical Monitor Approval	
02-Oct-2017 20:16 G	MT+0100	PPD	Nonclinical Scientist Approval	
05-Oct-2017 17:57 G	MT+0100	[name]	Clinical Development Approval	

Notes: (1) Document details as stored in ANGEL, an AstraZeneca document management system.

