2.1.3 Exploratory Objectives

2.2 Study Endpoints

2.2.1 **Primary Endpoints**

- 1. The incidence of AEs and SAEs.
- 2. The incidence of treatment-emergent AEs of special interest (AESIs) as follows:
 - Thrombotic and embolic events
 - Hepatic function abnormality (meeting the definition of Hy's Law [HL]; see Section 5.6.2)
 - Anaphylaxis and serious hypersensitivity reactions
 - Infusion-related reactions

- Immune complex disease
- Serious and/or opportunistic infections (including but not limited to reactivation of latent viral infection [varicella zoster (VZ), herpes simplex virus (HSV), EBV, CMV] and TB)
- 3. Vital signs, laboratory parameters (including coagulation parameters), electrocardiograms (ECGs), and physical examinations.

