3.1.3 Dose Escalation and Cohort Progression

Cohorts 1 to 3 will start sequentially, with escalation from Cohort 1 to Cohort 2 and Cohort 2 to Cohort 3 confirmed by a Dose Escalation Committee (DEC) comprised of MedImmune study team members and the Study Global Chief Investigator, who will assess in a blinded fashion the safety/tolerability data after the last subject in a cohort completes Day 29 (Week 4) of treatment and has AE/safety laboratory data available at that time point. There will be a total of three DEC meetings during the study; the first DEC meeting will only review data from Cohort 1 whereas the second DEC meeting will review cumulative safety data from first two dose cohorts being tested to date. The third DEC meeting will constitute a thorough evaluation of the cumulative safety and tolerability data for Cohorts 1 and 2 in addition to the data up to Day 85 for Cohort 3. While this review will not pertain to a dose escalation, it will contribute to the decision to instigate Cohort 4 (see below).

After the last Cohort 3 subject completes the Day 85 (Week 12) assessments, the primary analysis will be conducted to include safety, tolerability, PK, ADA, biomarker, and clinical response. Based on the outcome of this analysis, a fourth cohort will be included to better understand the dose (exposure)-response relationship.

If one or more of the following criteria are met, dose escalation will be suspended and the event(s) will be fully evaluated:

- A subject dosed with MEDI4920 experiences a confirmed or suspected thromboembolic event during the evaluation period or follow-up period. If the thromboembolic event is initially reported as "suspected", because of the unavailability of sufficient information to support a definitive diagnosis at that time, the DEC will re-assess the event when complete clinical/laboratory information is provided by the study site. A diagnosis algorithm (adapted from Wells and Anderson, 2013; Section 10.5 [Appendix 5]), is recommended to be used for any case of suspected DVT or PE. This includes clinical pre-test probability, D-dimer, and available imaging results. Based on full evaluation of the data as well as the diagnosis algorithm, if a thromboembolic event is ruled out or considered unlikely, dose escalation can be resumed.

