4.1.3 Exclusion Criteria

Any of the following would exclude the subject from participation in the study. Site staff must contact MedImmune for consultation prior to enrolling, randomizing, or administering investigational product to any subject who deviates from these criteria:

- 1. A history of, or current inflammatory joint disease other than RA (eg, gout, reactive arthritis, psoriatic arthritis, seronegative spondyloarthropathy, or Lyme disease) or other systemic autoimmune disorder (eg, SLE, inflammatory bowel disease, scleroderma, inflammatory myopathy, mixed connective tissue disease, or other overlapping syndrome). Subjects with polymyalgia rheumatica will be excluded from the study.
- 2. Subjects with a medical history of confirmed venous thromboembolism or arterial thrombosis.
- 3. Subjects with risk factors for venous thromboembolism or arterial thrombosis (eg, immobilization or major surgery within 12 weeks before screening), prothrombotic status (including but not limited to congenital or inherited deficiency of antithrombin III, protein C, protein S, or confirmed diagnosis of antiphospholipid syndrome).
- 4. Subjects with clinically significant abnormal coagulation panel at screening (including but not limited to multiple and significant shifts in prothrombin time ratio, activated partial thromboplastin time (D-dimer, etc). In case of doubts in assessing coagulation abnormalities as being clinically significant, the investigator may contact and discuss with the study medical monitor.

- 5. RA functional class IV, presence of severe systemic comorbidities (extensive vasculitis, pericarditis, amyloidosis, lymphoma), hemochromatosis, IgG4-related diseases, auto-inflammatory syndromes including Still's and Felty's syndrome.
- 6. Active or recent history (within the last 10 years) of malignancies (except for nonmelanoma skin cancers and in situ cervical carcinoma, treated and considered cured).
- 7. Pregnancy or lactation.
- 8. Subjects with recent (within 12 months) or active hepatitis A infection as evidenced by clinical history and/or positive test for anti-hepatitis A antibodies.
- 9. Subjects who have a positive test for, or have been treated for hepatitis B, hepatitis C, or HIV infection. Regarding hepatitis B, any of the following would exclude the subject from the study:
 - Subjects positive for hepatitis B surface antigen (HbsAg)

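### Two safety rules still in force for Cohort 4 are wrong as written: a PE score of exactly 4 falls in both probability classes, and one branch for repeat potential Hy's Law cases points to the criteria-not-met process

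*Protocol*

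**What the plan says.** **Pulmonary embolism.** Protocol Section 3.1.3 says that the diagnostic algorithm "is recommended to be used for any case of suspected DVT or PE". Section 10.5.2 gives the PE score and two classes. The footnote to the score table sets *PE unlikely* at 4 or less and *PE likely* at 4 or more, and the bullets repeat both limits. For the unlikely class: "ie, score ≤ 4), and D-Dimer value is ≤ ULN, PE is excluded". For the likely class: "ie, score ≥ 4) or D-dimer value is > ULN, chest X-Ray will be performed".

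The class is used once more. If the V/Q scan or CTPA cannot be had or is equivocal, PE counts as likely, unless the subject is in the unlikely class "and D-dimer is > ULN at previous time points during the study, including at baseline". A closing default begins "Each situation that cannot be adjudicated using the algorithm above will be considered as" and ends with *PE likely* and suspension of dose escalation.

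**Repeat potential Hy's Law.** Section 10.4.6 opens: "This section is applicable when a subject meets PHL criteria on study treatment and has already met PHL criteria" at an earlier on-treatment visit. It asks whether the earlier episode was put down to the disease under study, or whether PHL was already met before treatment and at the first on-treatment visit. 'No' leads to Section 10.4.3.1, whose title is for criteria not met. 'Yes' leads to no action or, if there has been a significant change, to Section 10.4.3.2, whose title is for criteria met.

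**Link to the endpoints.** The second primary endpoint in Section 2.2.1 is "The incidence of treatment-emergent AEs of special interest (AESIs) as follows". Its list includes thrombotic and embolic events and hepatic abnormality meeting Hy's Law.

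**The concern.** A decision rule should give one answer for each subject. At a PE score of 4 the algorithm gives two, and one of them closes the case without imaging. Thromboembolism is the class risk: Section 1.1.1 reports that development of an earlier anti-CD40L antibody was halted because of it.

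In the liver appendix, a subject reaches the 'No' branch only by meeting PHL criteria again. The branch leads to an instruction to tell the study representative that the criteria were not met, which is false by the scope of Section 10.4.6. The milder process also goes to the case that needs more attention. A repeat episode not explained by the disease under study gets routine laboratory follow-up, whereas one so explained, with a significant change, gets the full process.

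**Working it through.** The plan states no figure for either rule, so there is none to reproduce. The check is whether the conflict can occur, and what each reading does.

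**1. Can the PE score equal 4?** Item points in Section 10.5.2:
- DVT signs or symptoms: 3
- alternative diagnosis less likely than PE: 3
- heart rate above 100: 1.5
- immobilization or surgery: 1.5
- prior DVT or PE: 1.5
- hemoptysis: 1
- active cancer: 1

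Seven yes/no items give 2^7 = 128 combinations. Those that sum to 4 are:
- 3 + 1: 2 × 2 = 4 pairs
- 1.5 + 1.5 + 1: C(3,2) × 2 = 6 triples
- total: 10 of 128

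This counts combinations; it is not a probability.

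**2. Which of these fit eligible subjects?** Section 4.1.3 excludes "Subjects with a medical history of confirmed venous thromboembolism or arterial thrombosis", and criterion 6 excludes most malignancy within 10 years. Dropping prior DVT/PE and active cancer leaves five items and 2^5 = 32 combinations. Those that sum to 4 are:
- DVT signs + hemoptysis: 3 + 1
- PE the likelier diagnosis + hemoptysis: 3 + 1
- heart rate + immobilization/surgery + hemoptysis: 1.5 + 1.5 + 1

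That is 3 of 32, all with hemoptysis.

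**3. What does each reading do at score 4?**

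| Situation | Read as unlikely | Read as likely |
|---|---|---|
| D-dimer at or below ULN | PE excluded | Chest X-ray |
| D-dimer above ULN | Chest X-ray | Chest X-ray |
| D-dimer above ULN, imaging unavailable or equivocal, D-dimer also raised earlier | Exempt from *PE likely* | *PE likely* |
| D-dimer above ULN, imaging unavailable or equivocal, D-dimer not raised earlier | *PE likely* | *PE likely* |

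The overlap changes the outcome in the first and third rows only.

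**4. Is it a reading error from the PDF?** Unlikely. The 'at least 4' limit appears in both the footnote and the bullet, while the plain 'greater than' sign before ULN in that same bullet survived. The DVT score in Section 10.5.1 uses at most 1 and at least 2, which do not overlap, so exclusive classes were evidently intended.

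**5. Does a correction open a gap?** No. The attainable scores next to 4 are 3.5 (1.5 + 1 + 1) and 4.5 (for example 3 + 1.5).

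**6. Where does Section 10.4.6 lead?**

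| Answer | Sent to | What follows |
|---|---|---|
| No | 10.4.3.1 | Representative told criteria not met; later results followed as the protocol otherwise provides |
| Yes, no significant change | – | No action |
| Yes, significant change | 10.4.3.2 | Sponsor notified; medical monitor involved; monitoring to normal or baseline; cause investigated |

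Only the first row is wrong. It can plausibly be reached in this trial. Section 4.5.2.1 recommends withholding methotrexate when ALT or AST exceeds 3 × ULN and lets it be restarted after normalization. A second PHL episode after one attributed to methotrexate would answer 'No'. The documents give no frequency of repeat PHL, so none is estimated.

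**The case against.** The strongest reply is that other text already prevents harm.

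- **PE algorithm.** Read as a whole it leans to safety: the second bullet requires the X-ray at score 4, and the closing default makes unresolved cases *PE likely*. Section 4.1.6 stops dosing for a confirmed or suspected serious or severe thromboembolic event without mention of the score. The only consequence written into Section 10.5.2 is suspension of escalation, which is over.
- **Liver.** The central-laboratory alert in Section 10.4.2.3 still goes to the investigator and the sponsor's representative. Section 10.4.4 still requires review of every PHL case, and a delay beyond 3 weeks leads to an SAE report. Section 4.1.6 stops dosing for such an abnormality related to MEDI4920, so a repeat on treatment after a drug-attributed episode should be rare. Sections 10.4.3.1 and 10.4.3.2 each carry their own condition, so the pointer is evidently a wrong section number.

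All of this stands, and it limits the consequence. It does not make the text consistent. An investigator who stops at the first PE bullet has adjudicated the case and never reaches the default. Section 10.4.4 treats as PHL a case that Section 10.4.3.1 reports as not PHL.

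A reader might infer more, but the documents do not support it:
- *That primary endpoint counts are corrupted.* The liver AESI is Hy's Law, which is settled under Section 10.4.4. SAP Section 3.7.2 identifies AESIs by medical review of the AEs, not by the PE score.
- *That all repeat PHL cases are misrouted, or entered in the data as not PHL.* Only the 'No' branch is affected, and Section 10.4.3.1 asks for the representative to be informed, not for a data entry.
- *That the blinded Dose Escalation Committee's counting of MEDI4920 recipients is a third live fault.* The escalation decisions are past, and Cohort 4 (1000 mg) lies below a dose already given, so no result in this trial would change.

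**Conclusion.** Both errors are real and should be corrected while Cohort 4 is governed by this text, but they are narrow.

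The PE overlap matters only at a score of exactly 4, with either a normal D-dimer or unusable imaging after an earlier raised D-dimer. In eligible subjects it generally requires hemoptysis. Cohort 4 has 14 subjects, 10 of them on active drug. The 'generally' assumes that prior DVT/PE and active cancer stay rare after entry; either could newly arise on study.

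The Section 10.4.6 error removes the trigger for monitoring to normal and for the search for a cause in 'No' cases. It does not remove the Hy's Law decision. Its size cannot be given from the documents.

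No estimate, analysis or sample size is affected.

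**What to change.** **Section 10.5.2.** Make the classes exclusive: *PE unlikely* below 4, *PE likely* at 4 or more. This changes one sign in the footnote and one in the first bullet; the imaging step refers to the class by name and needs no edit. Setting *PE likely* above 4 would also remove the overlap, but the choice above follows the direction of the protocol's own default. The cost is an occasional extra chest X-ray in a subject with score 4 and normal D-dimer.

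**Section 10.4.6.** Point the 'No' branch to Section 10.4.3.2. This is one section number. Every repeat PHL case then gets the criteria-met follow-up, except a 'Yes' case without significant change, which the text exempts on purpose.

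Neither change adds subjects or scheduled visits.
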